12.5 Recording of Adverse Events

AEs spontaneously reported by the subject in response to the open question from the study personnel: “Have you had any health problems since the previous visit?” or revealed by observation will be collected at each visit; classified as mild, moderate, or severe; and recorded in the eCRF. When collecting AEs, the recording of diagnoses is preferred (when possible) to recording a list of signs and symptoms. However, if a diagnosis is known and there are other signs or symptoms that are not generally part of the diagnosis, the diagnosis and each sign or symptom will be recorded separately.

Subjects shall be encouraged to contact the investigator or a member of the clinical site staff at any time between visits concerning AEs or worsening of symptoms.

Abnormal and clinically significant lab values will be reported as AEs if they fulfill any of the SAE criteria or are the reason for discontinuation of treatment with the study drug. The principal investigator and the study biostatistician will establish the rules for what will constitute abnormal and clinically significant lab values based on established site-specific lab normal ranges. Adverse events, including abnormal lab values (clinically significant and clinically non-significant), will be reviewed monthly for trends by the principal investigator and the medical monitor. Should any abnormal lab values exceed rates described in the IB, the FDA will be notified within regulatory timelines. If deterioration in a laboratory value/vital sign is associated with clinical signs and symptoms, the sign or symptom will be reported as an AE and the associated laboratory result/vital sign will be considered as additional information. Wherever possible, the reporting investigator will use the clinical, rather than the laboratory term (e.g., anemia versus low hemoglobin value). In the absence of clinical signs or symptoms, clinically relevant deteriorations in non-mandated parameters will be reported as AE(s).

Any new or aggravated clinically relevant abnormal medical finding at a physical examination as compared with the baseline assessment will be reported as an AE

Disease progression can be considered as a worsening of a subject’s condition attributable to the disease for which the study drug is being studied. It may be an increase in the severity of the disease under study and/or increases in the symptoms of the disease. The development of worsening bipolar depression will be considered as disease progression and not an AE. Events (except for suicidal ideation or behavior) which are unequivocally due to disease progression will not be reported as an AE during the study.

12.6 Reporting of Adverse Events

All AEs and special reporting situations, whether serious or non-serious, will be reported from the time a signed and dated Informed Consent Form (ICF) is obtained until completion of the subject's last study-related procedure (which may include contact for follow-up of safety). Serious adverse events, including those spontaneously reported to the site-investigator from the time a signed and dated ICF is obtained until within 30 days after the last dose of study drug, must be reported using the Serious Adverse Event Form. CRO will evaluate any safety information that is spontaneously reported by a site investigator beyond the time frame specified in the protocol.

All events that meet the definition of a SAE will be reported as SAEs, regardless of whether they are protocol-specific assessments.

All AEs, regardless of seriousness, severity, or presumed relationship to study drug, must be recorded using medical terminology in the source document and the eCRF. Whenever possible, diagnoses will be given when signs and symptoms are due to a common etiology (e.g., cough, runny nose, sneezing, sore throat, and head congestion will be reported as "upper respiratory infection"). Investigators must record in the CRF their opinion concerning the relationship of the AE to study therapy. All measures required for AE management must be recorded in the source document and reported according to CRO instructions.

The sponsor assumes responsibility for appropriate reporting of AEs to the regulatory authorities. CRO, on behalf of the sponsor, will also report to site investigators all SAEs that are unlisted (unexpected) and associated with the use of the study drug. CRO will report these events to the designated IRB, on behalf of the sponsor.

12.6.1 Reporting of Serious Adverse Events

The EDC platform will provide a mechanism for sites to report SAEs, and for the site investigators and medical monitor to sign off on the SAE reports. Reportable SAEs will be sent to the FDA by the sponsor. CRO will notify sites of reportable SAEs, as outlined in Section 12.6.1.1.

When a SAE is discovered, it will be reported immediately (within 24 business hours) to the Medical Monitor, as described below. Serious adverse events will be reported within 24 business hours of the site's knowledge of the event to the IRB (see below). Reportable events which do not meet the criteria for an SAE will include (but will not be limited to): (a) pregnancy, and (b) clinically significant (in the judgment of the investigator) severe psychiatric complications. The site Principal Investigator will determine whether the event is study-related. All SAEs and reportable events will be reported within 48 business hours of [CRO] receipt of an SAE or other reportable event form to the sponsor, Medical Monitor, and the study site investigators.

12.6.1.1 Procedures for Assessing, Recording, and Reporting Adverse Events and Serious Adverse Events

Throughout the duration of the study, the Investigator will closely monitor each subject for evidence of drug intolerance and for the development of clinical or laboratory evidence of adverse events. All adverse events (expected or unexpected) which occur during the course of the study, whether observed by the Investigator or by the subject, and whether or not thought to be drug-related, will be reported and followed until resolution or until they become stable.

The description of the adverse event will include description of event, start date, stop date, intensity, if it was serious, relationship to test drug, change in test drug dosage, if the subject died, and if treatment was required.

Events will be coded to one of the following intensity categories below:

Severity	Definition
Mild	Awareness of signs or symptoms, but no disruption of usual activity
Moderate	Event sufficient to affect usual activity (disturbing)
Severe	Event causes inability to work or perform usual activities (unacceptable)

Events will be coded into one of the following causality categories as defined below:

Category	Definition
Unrelated	Clearly and incontrovertibly due only to extraneous causes, and does not meet criteria listed under possible or probable.
Unlikely	Does not follow a reasonable temporal sequence from administration. May have been produced by the subject's clinical state or by environmental factors or other therapies administered.
Possible	Follows a reasonable temporal sequence from administration, but may have been also produced by the subject's clinical state, environmental factors or other therapies administered.
Probable	Clear-cut temporal association with administration with improvement on cessation of investigational medicinal product or reduction in dose. Reappears upon rechallenge. Follows a known pattern of response to the investigational medicinal product.

Adverse events with the causality assessed as unrelated or unlikely are categorized as not related to study medication.

Adverse events with the causality assessed as possible or probable are categorized as related to study medication and are called adverse drug reactions.

All SAEs must be reported immediately (no more than 24 hours after becoming aware of the event). The investigator must complete the SAE Report Form and notify according to the Serious Adverse Event Report Form Instructions.

13. STATISTICS

The study analyses will be conducted in a GCP environment (ICH E6). All analyses will be pre-specified in a Statistical Analysis (SAP) prior to beginning subject enrollment.

13.1 Study Design

This is a two-stage design with two pre-defined interim looks during the second stage. The first stage is a direct assignment to Ketamine while the second stage is a randomized phase for those subjects following a documented Ketamine response.

13.2 Randomization

Following the documented observance of a therapeutic response to intravenous ketamine as defined by a 25% or greater reduction in the MADRS score and a score of < 3 on the C-SSRS, at 24 hours post infusion, patients will be randomized 2:1:1 to either a fixed dose combination of DCS + lurasidone (NRX-101), to an identical capsule containing placebo+lurasidone, or to an identical capsule containing placebo. Site blocking will be used to ensure that treatment and control groups are balanced per site.

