6.2 Methods

[figure not shown]
In Stage 1 eligible subjects will initially receive an infusion of open-label ketamine 0.5mg/Kg. Those who do not respond to ketamine infusion as measured by a $\geq 25\%$ improvement in the MADRS subset on the BISS and a reduction in C-SSRS suicidal ideation to ≤ 3 at 24 hours post infusion will be withdrawn from the study and treated according to standard of care for subjects with suicidal ideation or behaviors.

Subjects who respond successfully to ketamine infusion, as defined above ($\geq 25\%$ improvement in the MADRS subset of the BISS and C-SSRS ≤ 3) at 24 hours post infusion will proceed to Stage 2 and be randomized to either experimental drug NRX-101 (DCS + lurasidone), lurasidone alone, or placebo. Efficacy data will be collected for the subjects responding to ketamine through 6 weeks or until earlier rescue.

Subjects may be terminated from the study and rescued with alternative therapy at any time if, in the opinion of the investigator, subjects have a significant safety risk for clinical deterioration or suicide.

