8.1.6 Randomization

Subjects will be assessed in person 24 hours post-infusion for response to ketamine. Those who do not respond will be provided standard of care for ongoing suicidal ideation. Following the documented observance of a therapeutic response to intravenous ketamine as defined by a 25% or greater reduction in the on the MADRS subset of the BISS score and a score of ≤ 3 on the C-SSRS at 24 hours post infusion, subjects will be randomized 2:1:1 to either a fixed dose combination of experimental drug NRX-101 (DCS + lurasidone), or to an identical capsule containing placebo + lurasidone, or to an identical capsule containing placebo. Randomization blocks will be allocated at the site level to ensure that treatment and control groups are balanced per site. An Interactive Web Response System will be used.

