8.1.8 Post Ketamine Infusion Follow-Up

Subjects who are non-responders at 24 hours following the start of the ketamine infusion will be withdrawn from the study and treated according to the site’s standard treatment procedure. Non-response is defined as less than a 25% reduction on the MADRS subset of the BISS score and a score of ≥ 4 on the C-SSRS.

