8.2.3 Randomization phase

Following the documented observance of a therapeutic response to IV ketamine as defined by a 25% or greater reduction in the baseline MADRS and a C-SSRS ≤ 3 at 24 hours post infusion, subjects will be randomized 2:1:1 to either a fixed dose combination of experimental drug NRX-101 (DCS + lurasidone) or to an identical capsule containing placebo + lurasidone or to an identical capsule containing placebo. Institution balancing will be used to ensure that treatment and control groups are balanced with stratification according to C-SSRS 24 hours post-infusion (1, 2). Subjects who respond to ketamine will be followed for 6 weeks or until they require additional treatment.

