classification instrument C-SSRS. The C-SSRS tool was first developed for a prospective national study of treatment for adolescent suicide attempts. C-SSRS was developed by reliance on evidence stemming from two decades of research. It contains a 1-to-5 rating scale for suicidal ideation of increasing severity (from a “wish list to die” to an “active thought of killing oneself with plan and intent”), in contrast to C-CASA, which only has one ideation item. (IOM, 2010) The time frame is for both lifetime and the past six months for the Baseline/Screening scale and since the last visit for the Since Last Visit scale.

Brief Psychiatric Rating Scale (BPRS) (Overall & Gorham, 1962): The BPRS is an 18-item clinician rated scale that is used to assess a range of psychotic and affective symptoms, rated from both observation of the subject and the subject’s own report. It has been widely used to measure change in pharmacologic and nonpharmacologic treatment trials and provides a rapid and efficient evaluation of treatment response in clinic drug studies and in clinical settings. Only the 4-item positive symptom subscale BPRS+ (i.e., suspiciousness, hallucinations, unusual thought content, and conceptual disorganization) will be used in this study. It is highly sensitive to change, and excellent inter-rater reliability can be achieved (i.e., ICC>.80) with training and a standard interview procedure. Concurrent validity has been established by $r=.92$ between the positive symptom subscale and the corresponding subscale of the Positive and Negative Syndrome Scale, and sensitivity to change has been demonstrated by significant associations in change between the BPRS total score and the CGI and the HDRS.

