9.3 Randomization/Method of Assigning Subjects to Treatment

Following the documented observance of a therapeutic response to intravenous ketamine as defined by a 25% or greater reduction in the MADRS score and a score of ≤ 3 on the C-SSRS, at 24 hours post infusion, patients will be randomized 2:1:1 to either a fixed dose combination of DCS + lurasidone (NRX-101), to an identical capsule containing placebo+lurasidone, or to an identical capsule containing placebo. Site blocking will be used to ensure that treatment and control groups are balanced per site.

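### Section 13.2 requires C-SSRS < 3 for randomisation where Sections 6.2, 8.1.6, 8.2.3 and 9.3 require ≤ 3, so the entry status of a level-3 ketamine responder is contradictory

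*Combined protocol and SAP*

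**What the plan says.** Section 13.2, in the statistics chapter, makes randomisation conditional on "a 25% or greater reduction in the MADRS score and a score of < 3 on the C-SSRS" at 24 hours. Section 9.3 carries almost the same sentence with a different symbol: "a 25% or greater reduction in the MADRS score and a score of ≤ 3 on the C-SSRS". Three other statements of the criterion agree with 9.3:

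- Section 6.2: "improvement in the MADRS subset of the BISS and C-SSRS ≤ 3"
- Section 8.1.6: "a score of ≤ 3 on the C-SSRS at 24 hours post infusion, subjects will be randomized 2:1:1"
- Section 8.2.3: "a C-SSRS ≤ 3 at 24 hours post infusion"

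Section 8.1.8 approaches it from the other side. The C-SSRS part of its non-response definition is "a score of ≥ 4 on the C-SSRS".

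The 24-hour C-SSRS value is also used as a factor. Its levels are given as (1, 2) for stratification in 8.2.3, and as (1, 2) for covariates in 8.2.5.2.3, 11, 13.7.2, 13.10.6 and 13.10.8. Section 13.10.4 specifies the primary proportional hazards model and the MMRM with levels 1, 2 or 3.

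**The concern.** The criterion is the gate between the open-label ketamine stage and the randomised comparison. If two versions are in force, whether a level-3 subject is randomised depends on which section was used to build the IWRS or to brief the Medical Monitor, who confirms responders before randomisation (13.8.1).

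Three things depend on it:

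- **Who enters Stage 2.** Level 3 is one step below the relapse cut-off of 4 (8.2.5.1.1, 13.5.1). Admitting or refusing these subjects could therefore shift the event rate.
- **Who is eligible for the per-protocol set.** Sections 6.4 and 13.3 both restrict that set to eligible subjects. If sites randomise at ≤ 3 while 13.2 stands, the eligibility of every level-3 subject could be disputed after the data are seen.
- **What the 70% response rate means.** Section 13.8.2 builds the enrolment projection on it but names no C-SSRS cut-off.

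**Working it through.** **Step 1: how far apart are the two rules?** Section 8.2.6.1 says of the C-SSRS: "It contains a 1-to-5 rating scale for suicidal ideation of increasing severity". On whole-number levels, < 3 admits levels up to 2, and ≤ 3 admits levels up to 3. The rules differ by exactly one level.

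**Step 2: follow one subject.** Take a 24-hour C-SSRS of 3 with a MADRS fall of at least 25%.

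| Section | C-SSRS rule | Status of this subject |
|---|---|---|
| 6.2, 8.1.6, 8.2.3, 9.3 | ≤ 3 | meets response, randomised |
| 13.2 | < 3 | does not meet response |
| 8.1.8 | non-response at ≥ 4 | not a non-responder |

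If 13.2 were followed literally, this subject would be neither a responder by 13.2 nor a non-responder by 8.1.8.

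**Step 3: reproduce the plan's projection.** Inputs from 13.8.1, 13.8.2 and Table 12: 192 enrolled, 8% Stage 1 loss, 70% response, 124 randomised (62 + 31 + 31).

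- 192 × (1 − 0.08) = 176.6, stated as 177
- 177 × 0.70 = 123.9, stated as 124
- Backwards: 124 / 0.70 / 0.92 = 192.5, stated as 192

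The projection reproduces to within rounding.

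**Step 4: what would < 3 do to it?** Let f be the share of ≤ 3 responders who sit exactly at level 3. The documents do not give f, so 10%, 20% and 30% are assumptions. A second assumption is that the 70% was defined at ≤ 3.

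- Response rate under < 3 = 0.70 × (1 − f)
- Enrolment for 124 responders = 124 / [0.70 × (1 − f)] / 0.92

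| f | Level-3 subjects among 124 | Response rate | Responders from 177 | Enrolment for 124 |
|---|---|---|---|---|
| 10% | 12 | 63% | 111.5 | 214 |
| 20% | 25 | 56% | 99.1 | 241 |
| 30% | 37 | 49% | 86.7 | 275 |

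Rounding up at each stage instead gives 215, 242 and 277. If the 70% was defined at < 3, the projection already excludes level 3, and < 3 adds nothing to the 192.

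**Step 5: does the text elsewhere settle it?** The factor levels point both ways. Levels (1, 2) are what a < 3 rule would produce. Levels (1, 2, or 3) in 13.10.4 are what a ≤ 3 rule would produce. How the factor is levelled is a separate matter, but the split shows that the inconsistency is not confined to one symbol in 13.2.

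**The case against.** The strongest reply is that nothing differs in the source and an underline beneath the symbol was lost when the PDF was read. There is some support for this. The alternative hypothesis has > in 13.4.1 but ≥ in 5.1. The top age band reads >40 in 13.10.4, 13.10.6 and 13.10.8 but ≥40 in 13.7.2. Table 3 builds a plus/minus sign by underlining. Against it, ≥ survives in 13.5.1 and 13.7.2, and a lost underline cannot explain why the factor levels differ in plain digits. The possibility stands, unproven.

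The second reply is that 13.2 is outvoted. Four operative sections say ≤ 3, Section 8.1 describes stabilisation as level 3 or lower, and the primary model in 13.10.4 expects level 3. Sites would probably follow Sections 8 and 9. That lowers the practical risk. It does not remove the contradiction, because 13.2 is the statistical chapter's own account of who is randomised.

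The third reply concerns consequences, and it stands. A reader might infer that 13.2 makes level-3 subjects non-responders, but 13.2 does not define non-response. A reader might also infer that the threshold redefines the primary analysis population. Section 13.3 defines the Stage 2 ITT set by receipt of randomised treatment and a post-baseline efficacy assessment, with no C-SSRS cut-off. A level-3 subject who is randomised and meets those conditions is in it, so the effect is through entry only.

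**Conclusion.** The contradiction holds on the text supplied. A level-3 subject with at least a 25% MADRS reduction qualifies for randomisation under 6.2, 8.1.6, 8.2.3 and 9.3 but not under 13.2. This is a decision rule for entry to the randomised stage, so it is more than a typographical matter even if its origin is typographical. What is affected is entry to Stage 2, per-protocol eligibility and the meaning of the 70% rate.

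The size cannot be fixed from the documents. The range of about 214 to 275 against 192 rests on an assumed level-3 share of 10% to 30% and on the 70% rate having been defined at ≤ 3. It is a scenario in which 13.2 overrides the other four sections. It would be tempting to read it as a shortfall in the planned enrolment or a loss of power. The documents do not support that: the target of 124 randomised subjects is the same under either rule, and 13.8.2 already provides for more enrolment if response falls below 70%.

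**What to change.** Check the source file of 13.2 first, to see whether the symbol there is < or ≤. If the difference is real, the sponsor must reconcile the passages to one threshold before randomisation starts. That threshold should then appear identically in 13.2 and in every other statement of the criterion (6.2, 8.1.6, 8.2.3, 9.3), with the complementary non-response definition in 8.1.8 consistent with it. The IWRS and the Medical Monitor's confirmation should be programmed and briefed from that single text.

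Two follow-on checks depend on the choice: the levels of the 24-hour C-SSRS factor should match the values that randomised subjects can have, and 13.8.2 should state the C-SSRS cut-off to which the 70% refers. The rule also decides who is withdrawn to standard of care, so this review does not say which threshold is right.

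The cost is a few lines of text and a check of the IWRS specification. The target of 124 does not change. The enrolment projection would need revisiting only if the chosen threshold differs from the one behind the 70%.

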13.3 Study Populations

The study will have prospectively defined study populations including separate evaluability rules for the Ketamine treatment (Stage 1) and randomized treatment (Stage 2).

For Stage 1, the Intent-to-Treat population will include all subjects who received the Ketamine infusion and they have the 24 hours post-infusion efficacy assessments. The Per-Protocol population will include the subset of ITT subjects who were eligible, who had the 24 hour post-infusion efficacy assessments within 18 to 30 hours post the start of the initial infusion, and who had no major protocol violations. The Safety Population will include all subjects treated with Ketamine and with any post-baseline safety data.

For Stage 2, the Intent-to-Treat population will include all subjects who received the randomized study treatment and have any post-baseline efficacy assessments. The Per-Protocol population will include the subset of ITT subjects who were eligible, who have any post-baseline efficacy assessments within 1 day of scheduled visits through Day 7 and within 3 days of scheduled visits through Day 42, and who had no major protocol violations. The Safety Population will include all subjects as treated with study treatment and with any post-baseline safety data.

The ITT population will be used for the primary analyses. If <5% are to be excluded from the ITT population, then the analysis will not be performed for the PP population.

Every effort will be made to encourage patients to comply with the procedures and the assessments involved in study. Non-compliance will be tracked. Protocol violations will be reviewed in real time; prospective rules will be set for exclusions from the PP population.

